| Metagenomic sequencing | X | | X | | |
| Questionnaires¹ | | | | | |
| Risk perception and behavior | X ¹ | | | X | X |
| Socio-economic indicators | X ¹ | | | X | X |
| Use of resources (COVID-19 unrelated) | X ¹ | | | X | X |
| Adverse Events dedicated questionnaire | | X | X | X | X |
| Immune response | | | | | |
| Quantitative Ab anti-S IgG ⁵ | X | X | X | X | X |
| Qualitative Ab anti-N IgM+IgG ⁵ | X | | | | |
| Anti-SARS-CoV-2 sero-neutralization | X | X | X | X | X |
| Cytokine / chemokines | X | X | X | X | X |
| Anti-SARS-CoV-2 cell immunity | | X | | X ⁶ | X ⁶ |

Footnotes

Modular data capture according to level of commitment (level I, level II).

| | |
|----------|---|
| Level I | Assessments in level I are core and should be prioritized |
| Level II | Customized according to the feasibility of each cohort |

*3, 6 and 12 months counted from the 1st dose.

¹For centers able to follow patients since the administration of the first and second vaccination doses the baseline information and the risk perception behavior should be collected at one of these time-points, in the other cases such information should be collected during the first post-vaccination follow-up.

²The assessment at 2nd dose is mandatory in patients who will receive such dose within 8-12 weeks after first dose (current AstraZeneca vaccination schedule).

³If COVID-19 diagnosis, assessments reported in Table 1 are required.

⁴Relevant new medical events or worsening of previous conditions, including new malignancies (type of cancer, overall stage, Kaposi skin-visceral, Lymphoma localization-type, Leukemia lymphoid-myeloid acute-chronic), deep venous thrombosis, pulmonary embolism, infections (including a new SARS-CoV-2-infection during follow-up)

⁵At least one time-point at 1st and 2nd dose is required.

⁶At least one of the three timepoints (month 3, month 6, month 12) is required.

⁷At least one of the four timepoints (2nd dose, month 3, month 6, month 12) is required.

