For patients with a past and/or new diagnosis of SARS-CoV2 infection/COVID-19 disease a pre-established long-term follow-up including multiple diagnostic levels in order to adapt to all the participating cohorts is requested. A detailed overview of the schedule of the study visits and the clinical parameters to be recorded is shown in **Table 1**. Patients who have already had COVID, and new patients being diagnosed with COVID, who can be followed up to at least 12 months, and for whom data can be collected according to **Table 1** should be included. In specific fragile cohorts, such as children cohorts, virtual assessments are allowed.

For patients who have been or will be vaccinated against COVID-19 during the study period, a pre-established monitoring of safety and efficacy in terms of immunological response will be performed. A detailed overview of the schedule of the clinical and laboratory parameters to be recorded is shown in **Table 2**. Patients who have already been vaccinated, or will be vaccinated, who can be followed for 12 months, and for whom data can be collected according to Table 2 should be included. The monitoring should start from the days of first and second dose administration when possible (i.e. vaccination administered in the same center where the patient is followed for the fragile condition), alternatively patients will be monitored at 3±1, 6±2 and 12±3 months after the first vaccination dose.

- Vaccination safety will be assessed by a dedicated questionnaire (Annex 3) distributed to patients at baseline or during the first monitoring visit.

- Vaccination efficacy will be established analyzing the immune response at the predefined time-points. The humoral immune response to vaccination will be assessed by a serological assay able to detect anti-Spike and anti-Nucleocapsid antibodies as well as seroneutralization assays in sera samples. The latter will be useful to exclude possible natural infection at the baseline (1st/2nd dose, or first post-vaccination monitoring visit). The cytokine and cell-mediated immune response to vaccination will be assessed in a subgroup of patients by centralizing samples to a referral laboratory, according to local ethic rules and budget. The number of SARS-CoV-2 paucisymptomatic or symptomatic infection despite vaccination will be also assessed by SARS-CoV-2 detection in respiratory/saliva sample.

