ANNEX 3 – Questionnaire for monitoring of adverse events to COVID-19 vaccination

A) Demographics – Anamnesis

Age: _____

Sex: M F

Special population: HIV Cancer Solid organ transplant Haematological stem cell transplant

If solid organ transplant, please specify: Liver Kidney Heart Lung

Drug/food allergies: Y N If yes, please specify: _____

Previous serious adverse events to vaccination: Y N

Underlying diseases:

Renal Cardiovascular Asthma Diabetes mellitus Anaemia/Blood disorders

Seizure/Epilepsy

Other nervous system disease: Y N If yes, please specify: _____

Concomitant medications: _____

Blood transfusion in the last year: Y N

Treatment with immunoglobulin or antivirals in the last year: Y N

Other relevant conditions: _____

B) Adverse event report

First dose (dd/mm/yy): _____

Second dose (dd/mm/yy): _____

Clinical events after the first dose: Y N

Clinical events after the first dose: Y N

Headache: Y N

Asthenia: Y N

Fever ($\geq 38^{\circ}\text{C}$): Y N

Nausea: Y N

Vomiting: Y N

Lymphadenopathy: Y N

Tachycardia: Y N

Flushing: Y N

Syncope: Y N

Pruritus, erythema or pain in injection site: Y N

- Generalised urticaria: Y N
- Serious allergic events (anaphylaxis, angioedema): Y N
- COVID infection after vaccination: Y N
- Use of paracetamol or non-steroidal anti-inflammatory drugs: Y N
- Requirement for use of other drugs: Y N If Yes, please specify: _____
- Demyelinating disorders: Y N
- Encephalitis/Encephalopathy: Y N
- Peripheral neuropathy: Y N
- Muscular weakness and/or paralysis: Y N
- Visual impairment (including optic neuritis): Y N
- Walking disturbance: Y N
- Blood disorders (anaemia, thrombocytopenia, leukopenia): Y N
- Seizures/Epilepsy: Y N
- Weakness and/or paralysis of facial muscle: Y N
- Vasculitis: Y N
- Renal disorders: Y N
- Liver function disorders: Y N
- Cardiac disorders: Y N
- Other adverse events: Y N If Yes, please specify: _____

[figure not shown]
If yes (complete for each reported event): day of onset (dd/mm/yy): _____

hospitalization/emergency department admission/general practitioner visit: Y N

Description of the event (laboratory data/administered drugs/other relevant information):

Recovery: Y N

ANNEX 4 – WP6 Deliverable 6.1_Mapping of retrospective samples and development of standardized protocols for prospective sampling

WP6 Deliverable 6.1

Mapping of retrospective samples and development of
standardised protocols for prospective sampling

UANTWERPEN

Project Classification

| | |

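### The vaccine-safety form (Annex 3) has no risk window, new-or-worse item or reference period, so its crude organ-event frequencies cannot be separated from background disease

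*Protocol*

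**What the plan says.** Safety monitoring in Section 11 is written for the vaccinated: "For patients who have been or will be vaccinated against COVID-19 during the study period, a pre-established monitoring of safety and efficacy". The instrument is Annex 3: "Vaccination safety will be assessed by a dedicated questionnaire (Annex 3) distributed to patients at baseline or during the first monitoring visit". Centres that cannot start on the days of vaccination begin later: "alternatively patients will be monitored at 3±1, 6±2 and 12±3 months after the first vaccination dose".

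Table 2 (Section 3.2) gives a different timetable for the form. The row reads "Adverse Events dedicated questionnaire | | X | X | X | X": blank at the first dose, then marked at the second dose and at months 3, 6 and 12.

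Annex 3 is titled as a form for adverse events to COVID-19 vaccination. Part A records underlying disease, including renal, cardiovascular, blood and seizure disorders. Part B asks for both dose dates and then lists yes/no items such as "Blood disorders (anaemia, thrombocytopenia, leukopenia): Y N", with renal, liver, cardiac and seizure items in the same style. The lead question, "Clinical events after the first dose: Y N", is printed twice, and there is no matching line for the second dose. Each reported event gets an onset date. The form has no number of days after a dose, no new-or-worse condition and no causality field.

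The synopsis aims to evaluate vaccine safety in selected fragile populations; Section 7 aims to describe it.

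**The concern.** The special populations named on the form are HIV, cancer, solid organ transplant and stem cell transplant patients. Renal, hepatic, cardiac and blood disorders occur in them without any vaccine. A patient on chemotherapy who reports leukopenia nine months after dose 1 ticks the same box as one whose count fell in the week after it.

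Two consequences follow. A frequency read off the form has no defined time at risk, so it changes with the visit at which the form was completed, and cohorts with different visit timing are not comparable. A comparison across fragile groups would also partly reflect how ill each group is. Unvaccinated patients are followed under Section 8 but are not assigned the form, and the form does not ask about the same events before dose 1, so neither can serve as a reference.

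**Working it through.** **Plan's own figure.** The protocol gives no event rate, sample size or precision for vaccine safety, so there is nothing to reproduce. The calculation below is an illustration.

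**Inputs from the protocol.** The first monitoring visit is at 3±1 months, i.e. 2 to 4 months after dose 1. The form is scheduled to month 12±3 in Table 2, so the latest look-back is 15 months.

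**Assumptions.** Background incidence of 5, 10 or 20 per 100 patient-years for an organ event; no vaccine effect; a 42-day risk window, used only for scale.

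**Formula.** Share with at least one background event = 1 − exp(−r × t), with r per year and t in years. For example, at r = 0.05: 12 months gives 1 − exp(−0.05) = 4.9%, and 42 days gives 1 − exp(−0.05 × 42/365) = 0.57%.

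| Period counted | r = 0.05 | r = 0.10 | r = 0.20 |
|---|---|---|---|
| One 42-day window | 0.57% | 1.14% | 2.28% |
| Two 42-day windows (84 days) | 1.14% | 2.28% | 4.50% |
| Open look-back, 2 months | 0.83% | 1.65% | 3.28% |
| Open look-back, 4 months | 1.65% | 3.28% | 6.45% |
| Open look-back, 12 months | 4.9% | 9.5% | 18.1% |
| Open look-back, 15 months | 6.1% | 11.8% | 22.1% |

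**Ratios, open look-back to window.**
- First visit, one window: 0.83/0.57 ≈ 1.4 at 2 months and 1.65/0.57 ≈ 2.9 at 4 months. Counting part or all of a second window would lower these.
- 12 months, one window: 4.9/0.57 ≈ 8.5 at the lowest rate and 18.1/2.28 ≈ 8.0 at the highest, so about 8-fold.
- 12 months, two windows: 4.9/1.14 ≈ 4.3 and 18.1/4.50 ≈ 4.0, so about 4-fold. Two full windows need doses at least 42 days apart. The 8 to 12 week interval in a Table 2 footnote satisfies this; with a shorter interval the windows overlap and the ratio lies between 4 and 8.

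The ratios hardly depend on the assumed rate, because at low rates they approximate the ratio of the time spans. They do depend on which timetable governs. Under Section 11 alone (one distribution) the first-visit figures apply; the 12-month figures need Table 2.

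**What could be recovered later.** Dose dates and onset dates are on the form, so an analysis could apply a window afterwards. Whether an event was new or worse than before dose 1 is not on the form, and a tick in Part A shows history, not worsening. Table 2 schedules the whole blood count only at the two doses, so a later blood-disorder answer has no scheduled count beside it. If Section 11's single distribution governs, the form also supplies no later follow-up for a within-patient comparison.

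**The case against.** The strongest reply has four parts.

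- **A window can be set later.** Risk windows and counting rules often sit in a statistical analysis plan, which is not shown here, and the dates needed are collected. This stands for the window itself. It does not stand for the missing new-or-worse item, the duplicated first-dose line or the conflict over timing, which are matters for the protocol and the form.
- **A baseline exists.** Part A, the Table 2 rows for comorbidities and concomitant treatments, and the Section 11 baseline blood tests in immunocompromised cohorts all record prior state. This stands: underlying disease is recorded. Coverage is incomplete, because a Table 2 footnote lets some centres collect the baseline information at the first visit after vaccination. What is absent is a pre-dose count of the same events.
- **Another source records new or worsening events.** Table 2 has a row for relevant new medical events at all five time points, and its footnote covers worsening of earlier conditions. This stands and is useful for cross-checking, but Section 11 names Annex 3, not that row, as the safety instrument.
- **The aim is descriptive.** Crude frequencies can serve Section 7's wording, and a comparator is needed only for attribution. This stands in part. The synopsis says evaluate, and even a descriptive frequency needs a stated time at risk.

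A reader might also infer that every background event will be counted as a vaccine reaction, or that most of the reported rate will be background. The documents do not support this. Apart from the Annex 3 title, no text attributes the events to vaccination, no counting rule is stated, Section 12 does not list vaccine adverse events among its endpoint variables, and no background rates are given.

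**Conclusion.** The point holds in a limited form. Annex 3 yields post-vaccination event frequencies with no defined risk window, no record of whether an event is new or worse than before dose 1, and no reference period or unvaccinated comparison. Those frequencies cannot be attributed to vaccination, and they grow with look-back length.

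The growth follows from the design; its size rests on assumed background rates and an assumed 42-day window. On those assumptions the excess over a window is about 1.4 to 2.9 times at the 3±1 month visit and about 4 to 8 times over 12 months. The 8-fold figure should not be quoted alone, since it needs both the Table 2 timetable and a single window.

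The contradiction between Section 11 and Table 2 on when the form is given, and the repeated first-dose line, need no assumption. This is a change that should be made, because it is cheap and the new-or-worse information cannot be recovered from the form afterwards.

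**What to change.** 1. Reconcile Section 11 with Table 2 on when Annex 3 is completed, and correct the repeated first-dose line so that second-dose events are captured.
2. Add to Annex 3, for each reported event, an item asking whether it is new or worse than before dose 1.
3. In Section 11, pre-specify a post-dose risk window for each class of event, with lengths set by the sponsor. For organ events, compare the in-window rate with the same patient's later follow-up, using the dose and onset dates already collected. This requires the form to be repeated after the first visit, so it depends on step 1.
4. Report events outside the windows separately as medical events, cross-checked against the Table 2 row for relevant new medical events, and state that crude Annex 3 frequencies are not attributable to vaccination.

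The cost is wording in Section 11, one added item and one corrected line on the form. Late effects drop out of the attributed rate, though they stay in the all-events table. The within-patient comparison relies on onset dates that are partly recalled across visits months apart.

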24. Urine tests: pH, concentration, protein, glucose, red blood, white blood cell count
25. CD4 lymphocyte count; HIV-viral load; AIDS status
26. HIV-therapy: drug name and dose (only ongoing treatment); previous switch to other regimens for virological failure
27. Questionnaires to address cognitive status: Cognitive Failure Questionnaire (CFQ), Mini-Mental State Examination, Clinical Dementia rating Scale, Montreal Cognitive Assessment (MOCA).
28. Results of SARS-CoV-2 molecular test on amniotic fluid
29. Weight, height/length, cranial circumference, BMI
30. Type of transplant (heart, lung, kidney, liver, pancreas); single-combined; year of transplantation
31. Graft function: good, impaired, failure, rejection acute-chronic, recurrence of underlying disease, other
32. Immunosuppressive regimen: drug name and dose
33. According to Common Terminology Criteria for Adverse Events (CTCAE)
34. At least one of three timepoints (month 3, month 6, month 12) is required to perform metagenomics analysis.
35. At least one of the three timepoints (month 3, month 6, month 12) is required.

Table 2. Schedule of post-vaccination assessments

| | 1 st dose | 2 nd dose ² | 3 months (± 1 month)* | 6 months (± 2 months)* | 12 months (± 3 months)* |
|--|----------------------|-----------------------------------|--------------------------|---------------------------|----------------------------|
| Baseline information¹ | | | | | |
| Underlying fragile condition | X ¹ | X ¹ | | | |
| Healthcare setting (i.e. LTCF) | X ¹ | X ¹ | | | |
| Comorbidities | X ¹ | X ¹ | | | |
| Concomitant medical treatments | X ¹ | X ¹ | | | |
| Past and/or new COVID-19 disease ³ | X ¹ | X ¹ | X | X | X |
| Clinical evaluation | | | | | |
| Relevant medical new events ⁴ | X | X | X | X | X |
| Clinical symptoms suggestive of COVID-19 | X | X | X | X | X |
| Lab assessment | | | | | |
| Whole blood count | X | X | | | |
| CD4/CD8 count | X | X | | | |
| IgG level | X | X | | | |
| C3 level | X | X | | | |
| Immunology | | | | | |
| Immune - serology and type I IFNs autoantibodies | X | X | X | X | X |
| Immune - cytokine and chemokine | X | X ⁷ | X ⁷ | X ⁷ | X ⁷ |
| Immune - cellular | X | X ⁷ | X ⁷ | X ⁷ | X ⁷ |
| Microbiological tests-NP swabs | | | | | |
| Viral variant and metagenomics sequencing | X ⁵ | X ⁵ | X ⁶ | X ⁶ | X ⁶ |
| EDTA whole blood | | | | | |
| Genetic and epigenetic analysis | X | | X | X | X |
| Stool Sample (faeces or rectal swab) | | | | | |

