12. STUDY VARIABLES

Endpoint variables:

- Infection with SARS-CoV2 detected by RT-PCR on respiratory/saliva specimens;
- Reinfection and/or clinical relapse defined according to recent proposed definitions (7);
- Clinical spectrum of COVID-19 according to WHO mild, moderate, severe, and critical criteria (<https://www.who.int/publications/i/item/WHO-2019-nCoV-clinical-2021-1>);
- Duration of viable viral shedding in fragile patients diagnosed with COVID-19;
- Immune response in patients diagnosed with and/or vaccinated against COVID-19 assessed according to study protocol procedures (see above);
- All-cause mortality during the follow-up period;
- Change in basal clinical condition assessed by questionnaire on functional status and/or according to specific parameters of underlying fragile condition (i.e. graft function, cancer stage etc).

Baseline variables will include:

- Demographic data (sex, date of birth, ethnicity, blood group);
- Underlying conditions;
- Vaccination status against respiratory infectious diseases (i.e. Influenza, pneumococcus, BCG) if available.

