2.2 CHARACTERISATION OF SEROLOGICAL MARKERS OF SARS-COV-2 INFECTION (TASK 6.3)

This task will characterize the host antibody responses with quantitative serology (anti-S and anti-N) on Abbott, Roche, MesoScale Discovery (MSD), or similar platforms as well as (pseudo-) seroneutralisation assays. These assays will be performed on populations with various degrees of COVID-19 severity and vaccinated individuals, also with breakthrough infections.

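### Vaccine immune response is read to month 12, but anti-N is scheduled at the first dose only, so silent infections after dose 1 cannot be separated from vaccine response

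*Protocol*

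**What the plan says.** Protocol Section 11 defines how vaccine efficacy is judged: "Vaccination efficacy will be established analyzing the immune response at the predefined time-points". Patients not followed from the day of vaccination are seen later: "alternatively patients will be monitored at 3±1, 6±2 and 12±3 months after the first vaccination dose".

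After listing anti-spike, anti-nucleocapsid and neutralisation assays, the same bullet says: "The latter will be useful to exclude possible natural infection at the baseline (1st/2nd dose, or first post-vaccination monitoring visit"). Which assay is meant is not quite clear, but the time named is baseline. The bullet closes by saying that symptomatic and paucisymptomatic infections after vaccination will be assessed from respiratory or saliva samples.

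In Section 3.2, Table 2:
- quantitative anti-S IgG and neutralisation are marked at dose 1, dose 2 and months 3, 6 and 12;
- the row "Qualitative Ab anti-N IgM+IgG" is marked at dose 1 only;
- the row "Past and/or new COVID-19 disease" is marked at every visit, and a diagnosis triggers the Table 1 assessments;
- of the swabs at months 3, 6 and 12, at least one is required.

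Section 12 has one endpoint line for both exposures: "Immune response in patients diagnosed with and/or vaccinated against COVID-19 assessed according to study protocol procedures". Annex 4, Section 2.2 says the laboratory task will "characterize the host antibody responses with quantitative serology (anti-S and anti-N"), but names no visits. Annex 4, Section 3.2 draws serum at all five vaccination visits.

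**The concern.** Anti-S and neutralising antibody rise after infection as well as after vaccination. Anti-N can tell the two apart when the vaccine does not itself induce it. Here the outcome is measured for about a year, while the one named test that could reveal an unnoticed infection is scheduled at the start only.

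Take a patient with anti-S of 1000 at month 3 and 500 at month 6, who has a silent infection at month 8 and reads 2500 at month 12. The scheduled results show a 5-fold rise from month 6 (2500/500). Nothing in the named tests marks it as an infection.

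Three things are at stake. Waning looks slower than it is. Cohorts with more exposure look like better vaccine responders. A weak responder who is then infected can move up the distribution.

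**Working it through.** **The passages side by side**

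| Item | Dose 1 | Dose 2 | Month 3 | Month 6 | Month 12 |
|---|---|---|---|---|---|
| Anti-S IgG (Table 2) | yes | yes | yes | yes | yes |
| Neutralisation (Table 2) | yes | yes | yes | yes | yes |
| Anti-N (Table 2) | yes | – | – | – | – |
| New COVID-19 recorded (Table 2) | yes | yes | yes | yes | yes |
| Serum drawn (Annex 4, Table 3) | yes | yes | yes | yes | yes |

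A diagnosed infection leaves a dated record. An infection that causes no symptoms and is not swabbed leaves only higher anti-S and neutralisation results. A swab on a visit day shows infection present that day, not one that cleared between visits months apart. There is also a mismatch for late entrants: Section 11 lets the first post-vaccination visit serve as baseline, but Table 2 marks no anti-N there.

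**Size**

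The protocol gives no infection rate, detection rate, titre distribution or target for this endpoint, so it has no figure to reproduce. Every input below is an assumption.

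- c, share infected between baseline and month 12: 5% to 30%
- u, share of those infections not recorded: 30% to 60%
- b, fold rise in anti-S still present at month 12: 3 or 10, the same for all infected patients

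Share of month-12 samples carrying an unrecorded infection: s = c × u.
- Low: 0.05 × 0.30 = 0.015
- High: 0.30 × 0.60 = 0.18

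Inflation of the geometric mean: b^s.
- b = 3: 3^0.015 = 1.02 to 3^0.18 = 1.22
- b = 10: 10^0.015 = 1.04 to 10^0.18 = 1.51

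Waning, for a true month-12/month-3 ratio of 0.25 with month 3 unaffected, at s = 0.18: it reads 0.25 × 1.22 = 0.30 (b = 3) or 0.25 × 1.51 = 0.38 (b = 10).

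Two cohorts with identical vaccine response, 10% versus 30% infected, u = 60%: s is 0.06 versus 0.18, and the spurious ratio is b^0.12 = 1.14 (b = 3) or 1.32 (b = 10).

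Responder share, if every such infection makes the patient a responder: r + (1 − r)s. A true 50% reads 50.7% to 59%; a true 80% reads 80.3% to 83.6%.

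Upper bound, with recorded infections also left in (u = 100%): 1.06 to 1.39 for b = 3 and 1.12 to 2.00 for b = 10.

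**The case against.** The strongest reply is that follow-up infections are not ignored. New COVID-19 is recorded at every Table 2 visit and triggers the Table 1 assessments. Annex 4, Section 3.2 moves breakthrough cases to the COVID-19 sampling schedule. RT-PCR infection is an endpoint of its own in Section 12. Section 13 promises a procedure for censoring and allows time-dependent covariates. How to treat titres after a known infection is commonly settled in an analysis plan, which is not at hand. The Section 12 line is an entry in a list of variables and points back to Section 11, where infection and vaccination have separate procedures.

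All of this stands for diagnosed infections. A reader might infer that the protocol counts infection-boosted titres as vaccine response, with inflation up to 2.00. The documents do not say so: they are silent on it, and the 2.00 needs recorded, dated infections to be left in as well.

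The reply does not cover undiagnosed infections, because no analysis plan can remove what was not detected. It may be said that Section 11 also lists serology for screening, that Table 2 has a general serology row at every visit, and that Annex 4 plans anti-N. None of these assigns anti-N to a visit after dose 1. The row that names the test stops there, and Annex 4 gives way to the clinical protocol where they differ. If laboratories run anti-N at every visit anyway, the gap closes in practice, but the protocol does not require it.

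**Conclusion.** The point holds for undetected infections after dose 1: with the tests named in Table 2 they cannot be told from vaccine response, and they push month-12 anti-S upward, by different amounts in cohorts with different exposure. The illustrated inflation of 1.02–1.22 (3-fold boost) or 1.04–1.51 (10-fold boost) rests wholly on the assumed infection share, unrecorded share and persistence of the boost. At the low end it is negligible.

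For diagnosed infections the point is only that the protocol does not say they will be separated and that Section 12 joins the two responses in one line. Distortion of the genetic, methylation or microbiome contrasts is possible but not shown: Section 6 speaks of responders and non-responders without fixing a time-point, so late titres may not define those groups.

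**What to change.** 1. Extend the anti-N row of Table 2 to months 3, 6 and 12, using serum already drawn at those visits. Interpret it only for vaccines that do not themselves induce anti-N. This also settles the mismatch for patients whose baseline is their first post-vaccination visit.
2. Split the Section 12 endpoint into response to vaccination and response to infection, the latter including infection after vaccination.
3. For response to vaccination, use each patient's values up to the first RT-PCR-confirmed infection, recorded COVID-19 or new anti-N positivity. Report the uncensored result as a sensitivity analysis.

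Cost: this is a change to Table 2 with extra anti-N assays, not wording alone, but it needs no new blood draw. There will be fewer month-12 values, and the censoring may be informative if weak responders are infected more often; the uncensored analysis helps to show how much that matters. The sensitivity of anti-N in immunosuppressed patients is uncertain, so some silent infections will still be missed: the change reduces the bias and does not remove it.
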